Name of company: CLINUVEL Pharmaceuticals Ltd.	Name of finished product: SCENESSE®	Name of active ingredient: Afamelanotide 16mg
Title of study: A Proof of Concept, Phase IIa, Open Label Study to Evaluate the Safety of Afamelanotide in Patients with acute Arterial Ischaemic Stroke (AIS) due to Distal [M2 segment and beyond] Arterial Large Vessel Occlusion (LVO) or Perforator Occlusion and who are ineligible for Intravenous Thrombolysis (IVT) or Endovascular Thrombectomy (EVT).		
Study number: CUV801	Phase of development: IIa	
Principal investigators: [name]	Study centers: Alfred Hospital Melbourne	
Study period: 6 weeks		

Objectives: The primary clinical objectives are to
 
(i) evaluate the safety of afamelanotide in acute Arterial Ischaemic Stroke (AIS), and
 
The secondary objectives are to
 
(ii) identify changes in reperfusion of the ischaemic penumbra in AIS patients, specifically the ischaemic core and or the penumbral ischaemic zone (salvageable tissue).
 
(iii) assess neurological functions and activities of daily living in AIS patients.
		

Methodology:
 
This is an open label study of 42 days duration in patients with confirmed acute Arterial Ischaemic Stroke (AIS) (stroke) due to distal [M2 segment and beyond] large vessel occlusion (LVO) or perforator occlusion and who are ineligible to receive intravenous thrombolysis (IVT) or endovascular thrombectomy (EVT).
 
To determine eligibility for entry into the study, patients will undergo a screening evaluation on the day of admission following the AIS, Day 0. [REDACTED]
 
[REDACTED]
 
[REDACTED]
 
[REDACTED] Neurological functions will be assessed on Days 0, 1, 2, 3, 4, 7, 8 and 42 using the National Institutes of Health Stroke Scale (NIHSS). The modified Rankin Scale (mRS) will be used on Day 7 and Day 42 to compare to Day 0.
		

Assessments of adverse events (AEs) will be carried on Days 0, 1, 2, 3, 4, 7, 8 and 42.

Efficacy analysis will be undertaken upon completion of the study; exploratory statistical analyses will be performed; $\alpha \leq 0.05$ (two-sided) will be considered as significant.

No. of participants planned:

- **Six (6) acute AIS patients with distal [M2 segment and beyond] arterial LVO or perforator occlusion.**

Open label study: six (6) patients receiving afamelanotide.

Treatment:

Afamelanotide [REDACTED]
[REDACTED]

Diagnosis and main criteria for entry:

To be eligible to enter the study, patients must meet the following *inclusion criteria*:

- Male or female subjects with a diagnosis of first AIS due to distal [M2 segment and beyond] occlusion or perforator occlusion
- [REDACTED]
- Mild to moderate stroke severity [REDACTED]
- [REDACTED]
- Aged 18- 85 years
- Written informed consent obtained from patient and/or medical treatment decision maker prior to study-start (upon admission).

To be eligible to enter the study, patients must not meet any of the following *exclusion criteria*:

- Administration of intravenous thrombolytic therapy in distal occlusion as etiology of AIS
- Intervention by endovascular thrombectomy (EVT)
- [REDACTED]
- Any evidence of hepatic (defined as three times standard range) or [REDACTED]
- [REDACTED]
- [REDACTED]
- [REDACTED]
- [REDACTED]
- [REDACTED]
- [REDACTED]
- [REDACTED]

Test product:

Afamelanotide [REDACTED]

Dose: [REDACTED]

Mode of administration: Subcutaneous administration

Reference therapy:

None

Study Endpoints:**Primary Endpoints**

(i) Evaluate the safety of afamelanotide by monitoring and recording treatment-emergent adverse events (TEAEs) (on all days of administration and up to day 42).

Secondary Endpoints

- (i) Evaluate changes in reperfusion of the ischaemic core and the penumbral ischaemic zone (salvageable tissue)
- (ii) Evaluate neurological functions, cognitive functions, daily activities

Statistical Methods (exploratory):**Primary Endpoints****Safety Analyses:**

The number of participants with TEAEs will be summarized by Medical Dictionary for Regulatory Activities (MedDRA) preferred term and body system. TEAEs will be further summarized by intensity, seriousness, outcome and relationship to study drug. Participants who prematurely terminate treatment due to AEs related to study medication will be summarized.

Secondary Endpoints

An evaluation will be made of *changes in the reperfusion of the ischaemic core and the penumbral ischaemic zone* (salvageable tissue) [REDACTED]

In this exploratory analysis, the null hypothesis is formulated as:

H₀: there is no change to the ischaemic core and or penumbral ischaemic zone following the administration of afamelanotide 16mg.

Following changes observed from cerebral imaging, standard clinical outcomes will be monitored.

An evaluation will be made of

- (1) changes of neurological function as measured by NIHSS on Days 1, 2, 7 and 42 compared to baseline

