3.0 INTRODUCTION AND STUDY RATIONALE

Stroke is the second commonest cause of death globally and the leading cause of adult neurological disability¹. Acute arterial ischaemic stroke (AIS), due to arterial occlusion, accounts for 85% of all acute strokes whilst 15% of acute strokes are caused by an acute hemorrhage².

The outcome of AIS, both in terms of disability and survival, can be improved by reperfusion therapy using intravenous thrombolysis³ (IVT) and, or thrombectomy⁴ (mechanical endovascular removal of thrombus), in selected patients, where occlusion involves a proximal vessel of the circle of Willis. Both treatments are time dependent⁵ and at best only a significant minority of patients with AIS, [REDACTED] are eligible for reperfusion treatments. [REDACTED]

[REDACTED] Perfusion brain imaging, with computed tomography (CT) or Magnetic resonance imaging (MRI), has become the cornerstone of selecting AIS patients for reperfusion therapy and as such individualized patient treatment by using imaging as a surrogate for a ‘brain tissue clock,’ as opposed to arbitrary time since last seen well, in treatment decision paradigms⁶⁻⁹.

Stroke unit care has been shown to reduce mortality and dependence in AIS [REDACTED]

More than ever, effective neuroprotection – that may either facilitate more patients being suitable for timely reperfusion therapy by slowing the conversion of penumbra to core, or intrinsically attenuate the size of a threatened area of cerebral infarction is needed to aid assist in treating the global burden of disease due to AIS.

BLOOD BRAIN BARRIER (BBB)

It is well published that after a cerebrovascular accident (stroke) the damage to the blood-brain-barrier (BBB) includes decreased expression and altered organization of tight junction constituent proteins but also modulation of functional expression of endogenous BBB transporters.

Several hallmarks of pathology following ischaemic stroke is breakdown of the BBB, resulting in increased paracellular solute leak, modulation of transport proteins and endocytotic transport mechanisms, and inflammatory damage. Such barrier breakdown leads to a significant increase in paracellular permeability at the level of the cerebral microvasculature. These pathological derangements variably result in cognitive and motor impairments.

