5.5 Study Procedures

This will be an inpatient study (during hospital admission). [REDACTED]

[REDACTED] Patients may be discharged and will be asked to return to hospital for the rest of study visits. Patients will participate for a total of up to nine visits.

[REDACTED]

[REDACTED]

[REDACTED]

[REDACTED]

[REDACTED]

[REDACTED]

[REDACTED]

[REDACTED]

[REDACTED]

[REDACTED]

[REDACTED]

[REDACTED]

[REDACTED]

[REDACTED]

[REDACTED]

[REDACTED]

[REDACTED]

[REDACTED]

[REDACTED]

[REDACTED]

[REDACTED]

[REDACTED]

[REDACTED]

[REDACTED]

[REDACTED]

[REDACTED]

[REDACTED]

[REDACTED]

[REDACTED]

- | [REDACTED]
- | [REDACTED]
- | [REDACTED]
- | [REDACTED]
- | [REDACTED]

[REDACTED]

[REDACTED]

- | [REDACTED]
- | [REDACTED]
- | [REDACTED]
- | [REDACTED]
- | [REDACTED]
- | [REDACTED]

[REDACTED]

- | [REDACTED]
- | [REDACTED]
- | [REDACTED]

[REDACTED]

[REDACTED]

- | [REDACTED]
- | [REDACTED]
- | [REDACTED]
- | [REDACTED]

[REDACTED]

[REDACTED]

[REDACTED]

[REDACTED]

[REDACTED]

[REDACTED]

[REDACTED]

[REDACTED]

[REDACTED]

[REDACTED]

[REDACTED]

[REDACTED]

[REDACTED]

[REDACTED]

[REDACTED]

[REDACTED]

[REDACTED]

[REDACTED]

[REDACTED]

[REDACTED]

[REDACTED]

[REDACTED]

[REDACTED]

[REDACTED]

[REDACTED]

[REDACTED]

[REDACTED]

[REDACTED]

[REDACTED]

5.5.2 *Study Procedures Flowchart*

Please refer to the section [Study Flow Chart](#) of the protocol.

5.5.3 *Methods of Assessment*

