5.5.3.1.1 Evaluation of MRI imaging (CTP and DWI-FLAIR)

Background

For patients with acute arterial occlusion,

[REDACTED]

[REDACTED]

MRI diffusion weighted imaging (DWI) is accurate in the identification of acutely infarcted tissue.

[REDACTED]

Imaging Protocol

Standard care multimodal computed tomography (CT) will be performed on Day 0. [REDACTED]

[REDACTED]

MRI will be performed at Days 3(\pm 1) and 9(\pm 1) [REDACTED]

[REDACTED]

Efficacy of treatment

[REDACTED]

[REDACTED]

[REDACTED]

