5.7.2 Efficacy Assessment

5.7.2.1 Specification of Efficacy Endpoints

Primary Endpoints

- (i) *Evaluate the safety of afamelanotide* by monitoring and recording TEAEs (on all days of administration and up to day 42).
TEAEs will be recorded and coded as MedDRA Preferred Terms.

Secondary Endpoints

- (i) *Evaluate changes in the reperfusion of the ischaemic core and the penumbral ischaemic zone* (salvageable tissue) by quantitative analysis of hemodynamics:

[REDACTED]

- [REDACTED]
- [REDACTED]
- [REDACTED]

Upon completion of the study, each patient will generate efficacy after comparing the DWI-FLAIR on Days 3(\pm 1) and 9(\pm 1) with the CTP on Day 0 (Day of Admission).

[REDACTED]

[REDACTED]

[REDACTED]

[REDACTED]

[REDACTED]

5.7.3 *Safety Assessment*

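### A two-sided 0.05 test of no change after dosing in six uncontrolled stroke patients cannot show an afamelanotide effect, whether or not it is significant

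*Combined protocol and SAP*

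**What the plan says.** The Protocol Synopsis (Statistical Methods, Secondary Endpoints) gives the null hypothesis for imaging: "there is no change to the ischaemic core and or penumbral ischaemic zone following the administration of afamelanotide 16mg". The synopsis Methodology text sets alpha at 0.05 or less for the efficacy analysis ("two-sided) will be considered as significant") in the same sentence that calls the analyses exploratory.

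The design has no comparator. The synopsis lists no reference therapy, and section 5.3.2 describes a single open-label group of six. Section 5.7.4 bases the sample size on patient availability and gives no power statement.

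The baseline for the imaging comparison comes from section 5.7.2.1, not from the visible wording of the null hypothesis: "each patient will generate efficacy after comparing the DWI-FLAIR on Days" 3 and 9 (each ±1) with the Day 0 CTP. Section 5.5.3.1.1 says of Day 0 "Standard care multimodal computed tomography (CT) will be performed on Day 0", and of the follow-up method "MRI diffusion weighted imaging (DWI) is accurate in the identification of acutely infarcted tissue".

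The synopsis also lists NIHSS and mRS changes compared with baseline. Section 5.7 says the statistics will be descriptive and non-parametric. The specific test and much of the imaging efficacy text are redacted.

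**The concern.** The null hypothesis is about change over time, while the scientific hypothesis in section 3.0 is about what the drug does to the infarcted area. With no control group these are different questions, and the plan's own text supplies other reasons for change:

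- **Natural course.** Section 3.0 describes neuroprotection as working "by slowing the conversion of penumbra to core". Core and penumbra are therefore expected to change without the drug.
- **Change of method.** Day 0 is read on CTP and follow-up on DWI-FLAIR. A systematic difference between the two could appear as change.
- **Background care.** For NIHSS and mRS, section 3.0 says "Stroke unit care has been shown to reduce mortality and dependence in AIS", and section 5.5 says "This will be an inpatient study (during hospital admission"). If the 0.05 rule is applied to these scales, the same limit on attribution holds.

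The test is two-sided, so growth of the core would also reject the null. Conversely, if untreated core grows and there is no offset between methods, a drug that stops the growth makes the null true. At stake is a secondary result that is called significant in a proof-of-concept study and read as efficacy when it reflects infarct evolution, care or a change of scanner.

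**Working it through.** There is no power calculation in the plan to reproduce.

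**Inputs from the documents.** n = 6 (section 5.7.4); two-sided 0.05 (synopsis); one arm (section 5.3.2); non-parametric analysis (section 5.7). The named test is redacted, so I use the sign and Wilcoxon signed-rank tests as candidates. All drift, growth and offset values below are assumptions, because the documents give none.

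**1. What an exact test can reach.** With n = 6 there are 2^6 = 64 sign patterns.
- All six changes in one direction (rank sum W = 21): p = 2/64 = 0.03125.
- Next signed-rank value (W = 20): p = 4/64 = 0.0625.
- With n = 5 the minimum is 2/32 = 0.0625.

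Only six of six in one direction is significant. With five evaluable patients the exact test cannot reach 0.05.

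**2. Rejection with no drug effect, exact test.** Let q be the chance that one patient changes in the prevailing direction. P(reject) = q^6 + (1 − q)^6.

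| q (assumed) | q^6 + (1 − q)^6 | P(reject) |
|---|---|---|
| 0.50 (no drift) | 0.0156 + 0.0156 | 3.1% |
| 0.80 | 0.2621 + 0.0001 | 26% |
| 0.90 | 0.5314 + 0.0000 | 53% |
| 0.95 | 0.7351 + 0.0000 | 74% |

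**3. Does this depend on the redacted test?** Take the signed-rank test with a normal approximation and no continuity correction. The null mean is 6 × 7/4 = 10.5 and the SD is √(6 × 7 × 13/24) = √22.75 = 4.770.
- W = 20 gives z = 9.5/4.770 = 1.992 and p = 0.046, so the rejection region is W ≥ 20 or W ≤ 1.
- Its size without drift is 4/64 = 6.25%.
- For normal paired changes shifted so that q is 0.8, 0.9 or 0.95, simulation gives rejection of 42%, 74% or 90%.
- With the continuity correction, W = 20 gives p = 0.059 and the exact rejection region returns.

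The size of the problem differs between the tests, but the conclusion does not.

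**4. Does either outcome map to a drug effect?** Suppose the measure is core volume, untreated growth is 1 SD of the paired change, and the drug either does nothing or stops growth completely. Then q = Φ(growth + CTP-to-MRI offset), and the exact test gives:

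| Offset (assumed) | Drug does nothing | Drug arrests growth |
|---|---|---|
| 0 | q = Φ(1) = 0.841; 35% | q = 0.5; 3.1% |
| +1 SD | q = Φ(2) = 0.977; 87% | q = Φ(1) = 0.841; 35% |
| −1 SD | q = Φ(0) = 0.5; 3.1% | q = Φ(−1) = 0.159; 35% |

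In the first two rows a fully effective drug makes rejection less likely; in the third it makes it more likely. The documents give neither the sign nor the size of any offset, so neither rejection nor non-rejection identifies a drug effect.

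**5. Power to detect change itself.** For an assumed mean change of 0.5, 1.0 or 1.5 SD, the exact test rejects with probability 11%, 36% or 66% (for 1.0 SD: 0.841^6 + 0.159^6 = 0.355). Even as a test of change, a non-significant result says little.

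**The case against.** The best defence is that the plan does not visibly claim attribution. The null hypothesis is worded in terms of time, section 4.2 speaks of identifying and monitoring changes, and the analyses are called exploratory several times. No visible decision turns on p < 0.05, and no visible text says that a non-significant result will be read as lack of effect. The redaction is also wide: the imaging efficacy text in section 5.5.3.1.1, most of section 5.7.2.1 after the imaging comparison, and most of the efficacy analysis text in section 5.7.5.6. An interpretive limit could sit there, and how CTP and DWI-FLAIR are combined is not visible.

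Part of this stands. The harm is a likely misreading, not a specified wrong decision. The method-offset argument is conditional on how the two images are compared. The NIHSS and mRS argument is conditional on the 0.05 rule applying to them, and section 5.5 does not mention a stroke unit. The figures illustrate a mechanism and do not estimate its size in this trial.

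It does not remove the problem. The null hypothesis and the 0.05 rule are unredacted, and the exploratory label does not withdraw them. Section 5.7.2.1 calls the comparison with Day 0 efficacy. No redacted test or wording can supply a control group that the visible design excludes.

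**Conclusion.** The concern holds. As written, the imaging test addresses change over time in six uncontrolled patients. Rejection in either direction cannot be attributed to afamelanotide, and non-rejection does not show lack of effect. Under the assumed drift probabilities of 0.8 to 0.95, a drug with no effect would still give a significant exact test in 26% to 74% of such studies, and in 42% to 90% with the uncorrected normal approximation. These figures rest on assumed drift; the attribution point rests only on the absence of a control and on change being expected without the drug. The analysis is secondary and the primary safety endpoint is not affected, so this should be corrected but does not undermine the study's main purpose.

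**What to change.** In the synopsis, and in any matching redacted text of section 5.7:

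- Remove the no-change null hypothesis and the 0.05 significance rule for efficacy.
- Report imaging, NIHSS and mRS for each patient, with median and range at each time point.
- Note that the imaging method changes from CTP at Day 0 to MRI at follow-up.
- State that change from Day 0 will not be interpreted as a drug effect.
- If a p-value is kept, label it as a test of change from Day 0 only. If the test is an exact sign or signed-rank test, add that only six of six changes in one direction can reach 0.05.

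The cost is wording; no new data or patients are needed. The sponsor gives up calling an exploratory efficacy change significant.

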One of the most significant contributors to BBB breakdown in stroke is activation of proteinases such as matrix metalloproteinases (MMPs). This includes MMPs that are activated by hypoxia-inducible factor-1 α (HIF-1 α)-dependent mechanisms (i.e., MMP-2) and MMPs whose activation is triggered by cytokines (i.e., TNF- α , IL-1 β) such as MMP-3 and MMP-9.

Integrins, transmembrane glycoprotein receptors for the extracellular matrix, also play a significant role in BBB breakdown. Physiologically, integrins interact with constituents of the basement membrane (i.e., collagen IV, fibronectin, laminin, heparin sulfate proteoglycans such as perlecan) to regulate BBB permeability and transport. In ischaemic stroke, integrins are rapidly degraded, which leads to BBB breakdown and subsequent edema, inflammation, and exacerbation of stroke injury.

[REDACTED]

[REDACTED]

[REDACTED]

[REDACTED]

[REDACTED]

[REDACTED]

[REDACTED]

[REDACTED]

[REDACTED]

[REDACTED]

[REDACTED]

In 111 patients a longitudinal study showed that the effect of early plasma α -MSH on stroke outcome was more than a reflection of the stress response related to stroke severity and that maintenance of plasma α -MSH after stroke onset could be protective. Furthermore, a growing body of experimental data has shown that exogenous administration of α -MSH decreases infarct volume and improves stroke outcome¹⁶. There are numerous mechanisms by which α -MSH (and related neuropeptides) could improve stroke outcome, and these effects are mediated through 5 different melanocortin receptors (MCRs). Potent antipyretic properties of α -MSH, which could potentially be capitalized on in the treatment of stroke, are mediated through the MCR3/MCR4 receptor complex in the brain.

OBJECTIVES

The objective of this pilot study is to evaluate the safety of afamelanotide, identify changes in reperfusion in AIS patients, specifically the ischaemic core and/or the penumbral ischaemic zone (salvageable tissue) and assess neurological functions and activities of daily living in AIS patients.

SCIENTIFIC HYPOTHESIS

The scientific hypothesis is that the pharmacologic intervention with afamelanotide would positively affect the infarcted area in patients with AIS [REDACTED]

Afamelanotide is a potent synthetic analogue of the naturally occurring hormone, alpha melanocyte stimulating hormone (α -MSH).

[REDACTED]

[REDACTED]

[REDACTED]

[REDACTED]

[REDACTED]

[REDACTED]

[REDACTED]

[REDACTED]

[REDACTED]

[REDACTED]

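### The readable imaging null hypothesis, no change in core 'and or' penumbra, names no favourable direction, so rejecting or retaining it shows neither benefit nor harm

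*Combined protocol and SAP*

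**What the plan says.** The Protocol Synopsis, under Statistical Methods (exploratory), Secondary Endpoints, gives the only readable hypothesis for the imaging endpoint: "there is no change to the ischaemic core and or penumbral ischaemic zone following the administration of afamelanotide 16mg". The methodology part of the synopsis sets a two-sided significance level of 0.05 for the exploratory analyses. Section 5.7 says these will be descriptive and non-parametric; no test is named in readable text.

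The imaging objective and endpoint (synopsis, sections 4.2 and 5.7.2.1) speak of changes in reperfusion of core and penumbra, without a direction. On how the result is obtained, section 5.7.2.1 says that "each patient will generate efficacy after comparing the DWI-FLAIR on Days" 3 and 9 (each with a one-day window) with the Day 0 CTP. Section 5.5.3.1.1 says that DWI identifies infarcted tissue.

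The scientific case has a direction. Section 3.0 describes what neuroprotection might do: "slowing the conversion of penumbra to core, or intrinsically attenuate the size of a threatened area of cerebral infarction". The hypothesis in the same section is that "the pharmacologic intervention with afamelanotide would positively affect the infarcted area in patients with AIS".

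There is one arm (section 5.3.2) and six patients, a number set by availability (section 5.7.4). Several parts are blacked out: the end of the imaging sentence in the synopsis, the text under Efficacy of treatment in 5.5.3.1.1, the listed measures in 5.7.2.1, and much of 5.7 and 5.7.5.6.

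**The concern.** The rationale treats less conversion of penumbra to core as success. A drug that halted conversion completely would leave each core at its Day 0 size, and for the core component that is the null value. A drug that did nothing would let the core grow, and growth is the change that rejects the null. The core part of the hypothesis, taken alone, therefore runs against the scientific hypothesis.

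The penumbra part has a different weakness. At-risk tissue stops being at risk when it recovers and also when it infarcts. If follow-up penumbra is scored as what remains at risk, its disappearance does not show which of the two happened.

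Joining the two with 'and or' leaves open, until the data are seen, whether a change in one region is enough or both must change. Because a significance threshold is attached, a significant change could be reported as a signal of efficacy when the scans show infarct growth. A lack of change in core could likewise be read as a negative result when the cores were protected.

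**Working it through.** The plan has no derived figure to reproduce: the sample size of six comes from availability. The check is volume accounting followed by an exact test.

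**Inputs from the documents.** Six patients (5.7.4), one arm (5.3.2), two-sided level 0.05 and the null hypothesis (synopsis), and non-parametric analysis (5.7).

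**Assumptions not in the documents.**
- The test is an exact two-sided Wilcoxon signed-rank test.
- Each component is tested at 0.05 without adjustment.
- Follow-up penumbra is scored as residual at-risk tissue and has fully resolved by the follow-up scan.
- Illustrative Day 0 volumes are core 5, 8, 10, 12, 15, 20 mL and penumbra 10, 14, 21, 25, 33, 42 mL (mean 145/6 = 24.2 mL).

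**Formulas.** Let C0 and P0 be Day 0 core and penumbra, and s the fraction of penumbra saved.
- Follow-up infarct = C0 + (1 − s)P0
- Core change = (1 − s)P0
- Penumbra change = 0 − P0 = −P0, whatever s is
- Salvaged fraction = 1 − (follow-up infarct − C0)/P0 = s

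**Smallest attainable p.** If all six changes have the same sign, p = 2 × (1/2)^6 = 2/64 = 0.03125, which is below 0.05. With five evaluable patients it is 2/32 = 0.0625, which is not.

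**Results.**

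| Outcome in all six | Mean core change | p, core | Penumbra change | p, penumbra | Rejects if either region suffices | Rejects if both are needed | Salvaged fraction |
|---|---|---|---|---|---|---|---|
| All penumbra lost (s = 0) | +24.2 mL | 0.03125 | −100% | 0.03125 | yes | yes | 0% |
| Half saved (s = 0.5) | +12.1 mL | 0.03125 | −100% | 0.03125 | yes | yes | 50% |
| All saved (s = 1) | 0 | 1 (all changes zero) | −100% | 0.03125 | yes | no | 100% |

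Under the *either* reading all three outcomes reject, so the test does not discriminate. Under the *both* reading the most favourable outcome is the only one that fails to reject. The p-values and the −100% do not depend on the assumed volumes, provided that all six patients have some penumbra at baseline. Any s below 1 in all six gives the same core p of 0.03125, so p does not reflect how much was saved.

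For a single patient with assumed core 10 mL and penumbra 40 mL, full rescue gives an infarct of 10 mL and total loss gives 50 mL. Penumbra change is −40 mL both times. Core change is 0 and +40 mL respectively, so the signed core value does tell the two apart.

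**The case against.** The strongest objection is redaction. The text that defines the imaging measures is blacked out in the synopsis and in sections 5.5.3.1.1 and 5.7.2.1, and those measures could already be infarct growth or salvage. A reader might infer that the endpoint is scored without direction and cannot separate rescue from loss. The documents do not support that. The scoring cannot be seen, and the readable comparison of follow-up DWI-FLAIR with Day 0 CTP lends itself to a signed measure. This objection stands against any claim about the scoring. It does not reach the hypothesis sentence, which is legible in full and would have to be aligned with a directional measure if there is one.

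Second, a two-sided test keeps the sign of the estimate, and pairing it with a directional scientific hypothesis is ordinary practice. That is correct. The gap is that no readable text says which sign, or zero, is favourable.

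Third, a reader might infer that full protection means the whole null hypothesis is retained. It is the null value for the core only. On the assumption that penumbra has resolved, the penumbra component still changes, and the outcome turns on 'and or'. Nothing readable says that follow-up penumbra is measured at all, so the equal penumbra values are conditional.

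Fourth, a reader might think the core problem would survive the addition of a control arm. Largely it would not: protected cores could be compared with growing control cores, and the difference would favour the drug. The core problem is mostly the lack of a reference for expected growth.

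Last, the analysis is secondary and exploratory, with no readable decision rule tied to it. That limits the stakes but does not remove the mismatch.

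**Conclusion.** The point holds for the hypothesis and endpoint wording that can be read. The null hypothesis gives no favourable direction, no reference for expected core growth and no rule for 'and or', so neither rejection nor retention shows benefit or harm on its own. With six patients the core null can be rejected when every core grows (p = 0.03125), while six fully protected cores lie exactly on it.

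The p-value rests on an assumed signed-rank test. The penumbra result rests on the further assumption that residual at-risk tissue is what is scored and that it has resolved by follow-up. No conclusion is drawn about the redacted measures. The primary safety endpoint is unaffected. The wording is worth correcting because it costs little and prevents a statement about change from being read as one about efficacy.

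**What to change.** Reword the synopsis hypothesis and section 5.7.2.1 as follows, or align the hypothesis with the redacted measures if they are already directional.

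- State that rejecting no change is not evidence of efficacy, and that absence of core growth is a favourable result.
- Remove 'and or', and do not use stand-alone change in penumbra as an outcome.
- For each of the six patients, list signed infarct growth (follow-up infarct minus Day 0 CTP core, lower being better) and salvaged fraction (share of Day 0 penumbra not infarcted at follow-up). Summarise each by median and range.
- Do not test growth against zero as evidence of benefit. Infarct growth is the same quantity as core change, so testing it against zero would give the same p-values under a new name.

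The cost is a few sentences and a small derivation from scans already planned. The downside is that both measures depend on the CTP thresholds for core and penumbra and on comparing CTP with MRI. Without a control arm they remain descriptive.
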